6.2. Preparation, Handling, and Accountability

The investigator, investigational drug storage manager (for Japan), or designee must confirm appropriate temperature conditions have been maintained during transit for all study treatments received and any discrepancies are reported and resolved before use of the study treatment.

Only participants enrolled in the study may receive study treatment, and only authorized site staff may supply or administer study treatment. All study treatment must be stored in a secure, environmentally controlled, and monitored (manual or automated) area in accordance with the labeled storage conditions with access limited to the investigator, investigational drug storage manager (for Japan), and authorized site staff.

The investigator, investigational drug storage manager (for Japan), or designee is responsible for study treatment accountability, reconciliation, and record maintenance (ie, receipt, reconciliation, and final disposition records). Inventory and accountability records must be maintained and readily available for inspection by the study monitor and are open to inspection at any time by any applicable regulatory authorities. The investigator, investigational drug storage manager (for Japan), or designee must maintain records that document:

- Delivery of study drug and reference treatment to the study site.
- Inventory of study drug and reference treatment at the site.
- Participant use of the study drug and reference treatment, including pill counts from each supply dispensed.
- Return of study drug and reference treatment to the investigator, investigational drug storage manager (for Japan), or designee by participants.

The investigational product must be used only in accordance with the Protocol. The investigator (or investigational drug storage manager for Japan) will also maintain records adequately documenting that the participants were provided the specified study drug. These records should include dates, quantities, and any available batch or serial numbers or unique code numbers assigned to the investigational product and study participants.

Completed accountability records will be archived by the site. The investigator, investigational drug storage manager (for Japan), or designee will be expected to collect and retain all used, unused, and partially used containers of study drug and reference treatment until verified by the study monitor (unless otherwise agreed to by the sponsor). At the conclusion of the study, the investigator, investigational drug storage manager (for Japan), or designee will oversee shipment of any remaining study drug and reference treatment back to the sponsor or its designee for destruction according to institutional SOPs. If local procedures mandate on-site destruction of the investigational supply, the site should (where local procedures allow) maintain the investigational supply until the study monitor inspects the accountability records in order to evaluate compliance and accuracy of accountability by the investigative site. At sites where the study drug is destroyed before monitor inspection, the monitors rely on documentation of destruction per the site SOP.

Further guidance and information for the final disposition of unused study drug and reference treatment are provided in the Pharmacy Manual.

Administration instructions for the participant are provided in [Appendix H](#).

6.3. Measures to Minimize Bias: Randomization and Blinding

This is a double-blind, placebo-controlled study. Participants will receive ruxolitinib plus blinded study drug (parsaclisib or placebo). Participants, investigators, and the sponsor will remain blinded to each participant's treatment assignment (Group A or Group B) throughout the study. Emergency unblinding will occur if an AE requires the investigator to be made aware of the participant's treatment assignment (see emergency unblinding procedures in Section 9.6 and the Study Reference Manual).

A sponsor-designated statistician (in-house or contract) who is not part of the study team will be unblinded and will provide summary aggregated data by treatment group to the DMC for scheduled interim analyses or other DMC meetings, but individual participant data will remain blinded.

Block randomization with stratification for baseline platelet count (50 to $< 100 \times 10^9/L$ vs $\geq 100 \times 10^9/L$) and DIPSS category (high vs intermediate-2 vs intermediate-1) will be used. If a participant's platelet count is $< 50 \times 10^9/L$ at baseline, the platelet count at screening will be used for stratification/randomization. Participants will be randomly assigned to either Group A or Group B. All participants will be centrally assigned to study treatment using an IXRS. Randomization schedule will be generated by a sponsor-independent statistician and sent directly to the IXRS without provision to the sponsor. Before the study is initiated, the telephone number and call-in directions for the IVRS and/or the log-in information and directions for the IWRS will be provided to each site. Full details will be provided in the IXRS Manual.

The primary endpoint, spleen volume as measured by MRI (or CT scan in applicable participants), will be assessed by a blinded central reader and reviewer.

Study treatment will be dispensed at the study visits summarized in the SoA (see [Table 3](#)).

Returned study treatment should not be redispensed to the participants.

6.4. Dose and Requirement to Start Dosing After Crossover

After criteria for crossover have been met (early or for entire study) and sites have received notification that unblinding and crossover may occur, the crossover visit will be scheduled and dosing with parsaclisib will begin as long as the following hematology criteria are met based on a laboratory visit within 2 weeks of the planned parsaclisib start date:

- The platelet count is at least $50 \times 10^9/L$.
- The ANC is at least $0.5 \times 10^9/L$.

No more than 3 repeat assessments for platelet count and ANC are allowed. Participants who have received 1 or more platelet transfusions must have a platelet count $\geq 50 \times 10^9/L$ at least 7 days after the most recent platelet transfusion to qualify for crossover. Participants in whom the platelet count and/or ANC remain below these thresholds at the time of the later of (a) 4 weeks or (b) the next regularly scheduled study visit following the date at which it was

determined that crossover could occur will be discontinued from the study and that visit will constitute the EOT.

The dose of piasalisib will be 5 mg QD, taken in the morning, without regard to food.

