Contact IXRS	X	X	
Review criteria for crossover	X		
Concomitant medications	X	X	
Dispense parsaclisib and ruxolitinib	X	X	
Distribute reminder cards	X	X	
Collect study drug and reference treatment and review diary cards	X*	X†	*Parsaclisib/matching placebo and ruxolitinib bottles/blister packs to be collected. †Parsaclisib and ruxolitinib bottles/blister packs to be collected.
Transfusion history status	X	X	
Safety assessments			
Record AEs	X	X	Body systems with symptoms should be physically examined.
PJP	X	X	Prophylaxis continues from crossover visit through at least 2-6 months beyond the last dose of study treatment..
Efficacy assessments			
Spleen palpation	X	X	
Dispense and/or bring MFSAF v4.0 diary to visit	X	X	Diary continues only for early crossover before Week 24 and ends at Week 24.
MFSAF v4.0 diary	X	X	Diary continues only for early crossover before Week 24 and ends at Week 24.
ECOG performance status			
Laboratory assessments			
Serum chemistry	X	X	Then follow Table 5 .
Hematology	X	X	Then follow Table 5 .

Table 5: Schedule of Laboratory Assessments for All Participants

[figure not shown]
	Screening	Baseline	Day 1	End of Weeks 2, 6, 10, and 30 and Then Q12W	End of Weeks 4, 8, 12, 16, 20, and 24 and Then Q12W	EOT or Early Termination Visit	Safety Follow-Up 30-35 Days After Last Dose of Parsaclisib	Notes
Window				The window for laboratory-only visits is ± 3 days through Week 10 inclusive, and ± 7 days for laboratory-only visits beginning at Week 30 and Q12W				
Local laboratory assessments								
Serum chemistry	X	X*			X	X	X	*Should be collected as close as possible to Day 1 but may be drawn up to 3 days before first dose. Only 1 sample for baseline/Day 1 is required.
Hematology	X	X*		X	X	X	X	*Sample should be collected as close as possible to Day 1 but may be drawn up to 3 days before first dose. Only 1 sample for baseline/Day 1 is required. Note that if platelet count is $< 50 \times 10^9/L$ at baseline, the platelet count at screening will be used for stratification/randomization. See Section 8.1.3.
Coagulation panel	X				X*	X	X	*Required at Weeks 12 and 24 and Q12W thereafter.
Urine pregnancy test		X			X*	X*		All female participants of childbearing potential. *Pregnancy tests should be repeated if required by local regulations.

Table 5: Schedule of Laboratory Assessments for All Participants (Continued)

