	Screening	Baseline	Day 1	End of Weeks 2, 6, 10, and 30 and Then Q12W	End of Weeks 4, 8, 12, 16, 20, and 24 and Then Q12W	EOT or Early Termination Visit	Safety Follow-Up 30-35 Days After Last Dose of Parsaclisib	Notes
Window				The window for laboratory-only visits is ± 3 days through Week 10 inclusive, and ± 7 days for laboratory-only visits beginning at Week 30 and Q12W				
Bone marrow biopsy and aspirate analysis	X*				X†			Local pathologist to document findings. *Predose biopsy/aspirate is not required if biopsy has occurred within previous 2 months of screening as long as biopsy/aspirate and data are available for review by investigator and/or sponsor. †Week 24 and then every 24 weeks thereafter. Note: Samples of biopsy and aspirate will also be sent to a central vendor. The Laboratory Manual will describe procedures for biopsy and aspirate sample preparation and shipping. These samples for central analysis will only be collected in designated countries.
Central laboratory samples*								*The central laboratory is the sponsor or sponsor's designee.
Lipid panel (requires overnight fast)	X				X*	X		*Required at Weeks 12 and 24 and Q12W thereafter.
Virology and serology (hepatitis and HIV)	X							HBV, HCV, HIV
Virology - CMV	X				X*			*CMV measured at Weeks 4, 8, and 12 and Q12W thereafter.
Urinalysis	X				X*		X	*Required at Weeks 12 and 24 and Q12W thereafter.
Serum pregnancy test	X						X	All female participants of childbearing potential.
FSH level	X							To document hormonal menopause in relevant participants.

Table 5: Schedule of Laboratory Assessments for All Participants (Continued)

	Screening	Baseline	Day 1	End of Weeks 2, 6, 10, and 30 and Then Q12W	End of Weeks 4, 8, 12, 16, 20, and 24 and Then Q12W	EOT or Early Termination Visit	Safety Follow-Up 30-35 Days After Last Dose of Parsaclisib	Notes
Window				The window for laboratory-only visits is ± 3 days through Week 10 inclusive, and ± 7 days for laboratory-only visits beginning at Week 30 and Q12W				

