2.6.1.3. Potential Risks of PI3K Inhibition Based on Other Agents in Class

Idelalisib was approved by the FDA in July 2014 for treatment of relapsed/refractory follicular lymphoma and relapsed small lymphocytic lymphoma and for treatment of chronic lymphocytic leukemia in combination with rituximab. Severe toxicities seen with the use of this agent include hepatotoxicity (fatal and/or serious occurring in 16%-18%), fatal and/or serious diarrhea or colitis (14%-20%), intestinal perforation, pneumonitis, and infections (fatal and/or serious occurring in 21%-48%). PJP infection and CMV infection have also been reported ([Zydelig® 2018](#)).

Copanlisib was approved in 2017 for the treatment of relapsed follicular lymphoma. Clinically important toxicities observed with this agent include SAEs, including fatal infections (19%), usually pneumonia, Grade 3 or 4 hyperglycemia (41%), and Grade 3 hypertension (26%). Serious PJP occurred in 0.6% of patients treated with copanlisib ([Aliqopa® 2019](#)).

Duvelisib was approved in 2019 for the treatment of relapsed or refractory chronic lymphocytic leukemia, small lymphocytic lymphoma, or follicular lymphoma. Clinically important toxicities observed with this agent include fatal and/or serious infections (31%), fatal and/or serious diarrhea or colitis (18%), fatal and/or serious cutaneous reactions (5%), or fatal and/or serious pneumonitis (5%). Serious, including fatal PJP occurred in 1% of patients taking duvelisib, and CMV reactivation also occurred in 1% of patients taking duvelisib ([Copiktra® 2019](#)).

Participants in the present study will be monitored closely for the development of bacterial, fungal, or viral infections and will have treatment interrupted and dose reduced as appropriate. Participants will receive prophylaxis for PJP and will be monitored for CMV viremia during the study.

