4.1.1. Study Schedule/Procedures

There will be study site visits and laboratory-only visits in the study.

Participants will have a regularly scheduled study site visit at screening, baseline, Day 1, and at the end of 2, 4, 8, 12, 16, 20, and 24 weeks of treatment (ie, visits designated Week 2, Week 4, and so on) and then every 12 weeks thereafter if continuing on treatment in the extension period. During these visits, assessments including blood samples and spleen measurements will be performed. All serology, lipid profile, and urinalysis laboratory assessments will be analyzed by a central laboratory. Serum chemistry, hematology, and coagulation parameters will be assessed using local laboratories. [REDACTED]

Participants will have laboratory-only visits to collect hematology laboratory samples at Week 6, Week 10, and, if continuing beyond Week 24, every 12 weeks beginning with Week 30. Participants may visit a local laboratory or a location convenient to the participant for these interim hematology assessments provided that the laboratory data and corresponding normal ranges can be scanned and e-mailed to the investigative site; interim laboratory visits at the study site laboratory are preferred. Additional and unscheduled laboratory assessments may be performed at investigator discretion, including following changes in dose, or if laboratory parameters are at Grade 3 or Grade 4 levels based on CTCAE v5.0.

Participants who cross over (defined in the following text) will have 2 additional study site visits: the day of crossover and 4 weeks after crossover. Participants who have crossed over will otherwise remain on the same study schedule they were on prior to crossover. Note these crossover participants may not need to have the laboratory visit at Week 30 as this may coincide with the Week 4 post-crossover visit.

Participants will have an MRI of the upper and lower abdomen and pelvis to determine the spleen volume at baseline, Week 12, Week 24, and every 12 weeks thereafter through Week 144. A CT scan will be substituted for participants who are not candidates for MRI or when MRI is not readily available. [REDACTED]

Participants will complete an electronic symptom diary (MFSAF v4.0) daily from baseline through the Week 24 visit (total of 25 weeks).

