4.1.2. Unblinding and Crossover

When the last enrolled participant has completed the Week 24 assessments and the data entered by all sites for all participants has been verified and cleaned through the Week 24 visit (including imaging), the database will be frozen. The study will then be unblinded, and participants randomized to placebo will have the opportunity to cross over to begin receiving parsaclisib, together with continued ruxolitinib, as long as hematology parameters are adequate (see Section 6.4 for hematology requirements). Similarly, participants found to have been randomized to parsaclisib will continue treatment with parsaclisib, together with continued ruxolitinib, as long as the regimen is tolerated and the participant does not meet discontinuation criteria.

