
 • Exfoliative dermatitis (Grade 1) 	
Step 1: Interrupt parsaclisib or matching placebo until the toxicity has resolved.
 
Step 2: Restart parsaclisib or matching placebo at the next lower dose. Monitor as clinically indicated.

 • Exfoliative dermatitis (\geq Grade 2) 	
Permanently discontinue parsaclisib or matching placebo.

 • Intestinal perforation (any grade) 	
Permanently discontinue parsaclisib or matching placebo.

 • PJP 	
Interrupt parsaclisib or matching placebo. Permanently discontinue parsaclisib or matching placebo if PJP is confirmed.

 • CMV infection 	
Participants with CMV viremia without associated clinical signs of CMV infection should be carefully monitored. Consider interrupting parsaclisib or matching placebo for participants with CMV viremia and clinical signs of infection until the infection has resolved. Restart parsaclisib or matching placebo reduced by 1 dose level if approved by the medical monitor.

 • Varicella zoster infection 	
Interrupt parsaclisib or matching placebo. Restart parsaclisib or matching placebo only by approval of the medical monitor.

 • Any Grade 1 or Grade 2 toxicity unless otherwise specified. 	
Continue parsaclisib or matching placebo treatment and treat the toxicity; monitor as clinically indicated.

 • Any Grade 3 toxicity, if clinically significant and not manageable by supportive care unless otherwise specified. 	
Step 1: Interrupt parsaclisib or matching placebo for up to 2 weeks (14 days) until toxicity resolves to \leq Grade 1.
 
Step 2: Restart parsaclisib or matching placebo at the same dose. If assessed as related to parsaclisib or matching placebo, restart at the next lower dose. If interrupted for $>$ 14 days, contact the medical monitor for approval to restart parsaclisib or matching placebo. Monitor as clinically indicated.

 • Any recurrent Grade 3 toxicity after 2 dose reductions. 	
Discontinue parsaclisib or matching placebo administration and follow-up per Protocol. Exceptions require approval of sponsor.

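### The CMV schedule is not reset at crossover: nominally one scheduled test in the first 12 weeks on parsaclisib after a post-Week 24 crossover, against three after a Day 1 start

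*Protocol*

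**What the plan says.** Section 6.4 of the protocol states the laboratory conditions for the first crossover dose: "dosing with parsaclisib will begin as long as the following hematology criteria are met". The criteria are a platelet count of at least 50 × 10⁹/L (with a 7-day rule after platelet transfusion) and an ANC of at least 0.5 × 10⁹/L. Section 4.1.2 refers to the same hematology requirements. Section 2.6.1.2 adds a separate condition, that immune-related events have resolved for 2 weeks before parsaclisib starts.

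The CMV row of Table 5 has a screening sample and this note: "CMV measured at Weeks 4, 8, and 12 and Q12W thereafter". Section 4.1.1 fixes the calendar: "Participants who have crossed over will otherwise remain on the same study schedule they were on prior to crossover". Crossover adds two visits, on the day of crossover and 4 weeks later. The laboratory rows for those visits in Table 4 are serum chemistry and hematology, each annotated "Then follow Table 5".

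On CMV itself, Section 2.6.1.3 says: "Participants will receive prophylaxis for PJP and will be monitored for CMV viremia during the study". Table 11 (Section 6.7.2) says: "Participants with CMV viremia without associated clinical signs of CMV infection should be carefully monitored". At study entry, exclusion criterion 9 in Section 5.2 requires a negative CMV PCR.

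**The concern.** The plan tests Day 1 starters more closely for CMV in their first 12 weeks, then every 12 weeks. A placebo participant who crosses over starts parsaclisib for the first time but is already on the sparser part of the calendar. Table 4 does treat crossover as a new exposure for chemistry and hematology; it does not do so for CMV.

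CMV is among the serious infections that Section 2.6.1.2 reports with parsaclisib, and CMV infection is an adverse event of special interest in Section 9.5. Viremia without signs can only be found by testing, so Table 11's instruction to monitor it depends on the schedule. Crossover is offered to every eligible placebo participant once the study is unblinded. With about 440 randomized 1:1, that is at most 440 / 2 = 220 people. What is at stake is patient safety, not the efficacy comparison.

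**Working it through.** The plan states no figure of its own here, so the check is a count of scheduled tests.

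**Inputs**

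- CMV weeks (Table 5): 4, 8, 12, 24, 36, 48 and so on, on the original calendar.
- Calendar not reset at crossover (Section 4.1.1).
- Visit windows (Table 3): ±5 days for Weeks 4 to 24, ±7 days for extension visits.
- 4-week post-crossover visit: ±5 days (Table 4).
- Screening window: Day -35 to Day -8 (Table 3).

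**Nominal count.** Let x be the study week of the first parsaclisib dose. Count the CMV weeks in (x, x + 12].

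- Day 1 start (x = 0): Weeks 4, 8 and 12, so 3 tests.
- Crossover at x ≥ 24: tests are 12 weeks apart, so any 12-week interval of this form holds exactly 1. Counting for each day from Day 168 to Day 923 gives 1 on all 756 days.
- Earlier crossover: 3 tests at Week 2, 2 at Weeks 4 to 6, and 1 from Week 8. From Week 12 up to Week 24 the single test is Week 24.

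**Wait to the first on-drug test, and age of the last PCR.** For nominal visits at x ≥ 24, wait + age = 12 weeks.

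| Crossover week | Next CMV test | Wait (weeks) | Age of last PCR (weeks) |
|---|---|---|---|
| 24 | 36 | 12 | 0 |
| 26 | 36 | 10 | 2 |
| 30 | 36 | 6 | 6 |
| 34 | 36 | 2 | 10 |

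The Week 26 row is the protocol's own illustration. Section 4.1.1 says that the Week 30 laboratory visit may be unnecessary because "this may coincide with the Week 4 post-crossover visit", and 30 − 4 = 26. If crossover days were uniform over the 12-week cycle (an assumption), the wait would run from 1 to 84 days. Its mean would be (1 + 84) / 2 = 42.5 days, about 6.1 weeks.

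**With visit windows**

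- Consecutive extension visits are 84 ± 14 days apart, that is 70 to 98 days. The longest wait is 98 days, and 0, 1 or 2 tests can fall in the first 84 days.
- Week 26 illustration: 70 ± 7 days, that is 63 to 77 days.
- Day 1 start: tests at days 28, 56 and 84, each ±5. The first falls between days 23 and 33, and 2 or 3 fall in 84 days.

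**PCR age before the first dose.** At entry it is 8 to 35 days, from the screening window. At crossover it can be up to about 12 weeks.

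**After the proposed change.** The first on-drug test falls at 28 ± 5 days, so at most 33 days. The nominal count is 2 in 12 weeks, or 1 if the 4-week visit coincides with the routine draw (for example x = 32, where 32 + 4 = 36).

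**The case against.** The strongest reply is that no commitment is broken. Section 2.6.1.3 promises CMV monitoring without giving a frequency, Table 5 applies to everyone, and testing every 12 weeks is what all participants get after Week 12. That is right, and it is why this is a design improvement rather than an error.

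The Day 1 comparison is also not like for like. Day 1 starters begin two drugs at once, and ruxolitinib carries its own viral infection risk (Section 2.6.2.1). Someone crossing over after Week 24 has already taken ruxolitinib for that time, with CMV tests at Weeks 4, 8, 12 and 24. The documents never say that the early tests are there for parsaclisib alone. This weakens the case for full parity. But tests on ruxolitinib plus placebo say nothing about the first weeks after parsaclisib is added.

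The extremes need care. The longest wait and the oldest pre-dose PCR cannot occur together, because they sum to 12 weeks on nominal visits. Crossover near Week 26 need not be typical either, since general crossover waits for the last participant's Week 24 visit and data cleaning.

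Other safeguards exist: a CMV workup for Grade 2 or higher diarrhea, Table 11's rule for viremia with signs, stopping for clinically significant infection (Section 2.6.1.2) or for harm in the investigator's judgment (Section 7.1.1), and unscheduled tests (Section 8.6). These are triggered by symptoms or discretionary, so they do not provide routine detection of silent viremia.

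Yield is unknown. The protocol gives no CMV rate for parsaclisib; its only class figure is 1% reactivation with duvelisib. If that applied to 220 crossovers (an assumption about a different drug, and not a rate from routine PCR), about 220 × 0.01 = 2.2 cases would be expected. The absolute benefit may be small, which keeps the priority low.

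**Conclusion.** The concern holds. After a post-Week 24 crossover the plan schedules nominally 1 CMV test in the first 12 weeks on parsaclisib (0 to 2 with windows), against 3 after a Day 1 start (2 or 3). The longest wait to a first on-drug test is 98 days against 33. Crossover between Week 12 and Week 24 also has nominally 1 test.

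These are testing gaps, not estimates of harm. The conclusion assumes that the published Table 4 is complete in its laboratory rows, where no redaction is visible, and that Section 4.1.1 means what it says about the calendar. It is a point to consider for patient safety; no efficacy analysis, power or error rate is involved.

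**What to change.** Add a CMV PCR row to Table 4 with two samples:

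- one at the qualifying pre-crossover hematology draw, waived if a routine PCR was taken within the previous 35 days (the limit that the screening window implies at entry);
- one at the existing 4-week post-crossover visit.

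Handle positive results under the existing CMV rule in Table 11. Asymptomatic viremia needs no new hold rule, so the pre-dose sample serves as a current baseline rather than a gate on dosing. Optionally, add a sentence to Section 6.4 allowing the first dose to be deferred while an active infection is treated, within the window already there (the later of 4 weeks or the next scheduled visit).

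The cost is one table row and at most two extra samples per crossover participant, at blood draws already planned. CMV is a central test (Section 8.3.5.4) whereas hematology and chemistry are local, so those draws would need central collection and shipping. The change does not restore all three tests. Resetting the CMV clock fully would, but it needs a test 8 weeks after crossover, for which Table 4 has no visit. If the sponsor prefers the present schedule, the protocol should say why crossover starters need less early CMV testing than Day 1 starters.
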